Exploratory Endpoint. A subset of analyses will examine return visits to the ED (obtained via EDW query) and admission to the hospital for a complaint related to opioid pain reliever (ranging from mild, e.g., constipation to severe, e.g., respiratory depression). Additional analyses will be conducted to evaluate for possible misuse or inappropriate prescribing. Outcome indicators include: 1) opioid overlap (defined as opioid prescriptions that overlap by 7 or more days, including refills), 2) opioid and benzodiazepine overlap, 3) long acting/extended release opioid prescription written for acutely painful conditions 4) high daily opioid dosage (defined as a prescribed daily dose of 100 morphine milligram equivalents (MME) or greater) and 5) opioid dose escalation (measured as having a 50% or greater increase in mean MME per month twice during the year).^{91,92} These data will be obtained by a data pull via the Illinois

EHR-Based Medication Complete Communication (EMC²) Strategy to Promote Safe Opioid Use: A Physician Randomized Trial

Prescription Monitoring Program (ILPMP) at 1-year post initial ED prescription. Drs. [name] and [name] will conduct this data-pull. Patients PHI will not be sent to the ILPMP or any other state or pharmacy governing body to obtain these data.

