Patients with ED physicians randomized to the EMC² +SMS Text reminder arm will receive the above-described 5 components of the EMC² intervention, and also will receive daily text reminders for one week (7 messages) following the new prescription for an opioid pain reliever (only consented patients). The premise for the 1-week timeframe is to help patients remember precautions regarding safe use during the time they are taking the medication (average ED Rx for opioids is from pilot data is 18 tabs). Furthermore, SMS text reminders that would continue indefinitely are at risk for either being ignored, irritating patients, and/or adding an unnecessary expense to patients (i.e., patient does not have an unlimited texting plan, further challenging sustainability). Messages sent early in the week will focus on topics such as safe storage and use; those sent near the end of the week will focus on topics such as disposal and pill sharing. We will schedule EMC² text messages to arrive mid-day (12:00pm to 5:00pm), based on patient preference. (See appendix for sample text messages)

9.3 Procedures to monitor safety and minimize risk.

As a part of all of the time points of follow-up, the RAs will have a checklist of potentially dangerous behaviors related to opioids and if these items are noted in the course of data collection the RAs have a set protocol to follow. (see safety protocol attached)

9.4 The drug hydrocodone-acetaminophen is the topic of the research; however it is not being used in the research—the intervention is focused on education about this medication and the study will not change the drug, dose, frequency, quantity or refills that the ED physician selects in the course of their normal clinical care.

Sources of Materials:

Electronic Health Record (EHR): Patient information and outcomes will be extracted from the EHR (demographics, ED return visits and re-admissions). Re-admissions and re-visits to the hospital and ED data will be abstracted from medical records for all patients enrolled into the study, as well as all patients prescribed an opioid during the recruitment period of 18-months.

EHR-Based Medication Complete Communication (EMC²) Strategy to Promote Safe Opioid Use: A Physician Randomized Trial

Illinois Prescription Monitoring Program (ILPMP): We will obtain data from the ILPMP on medication fill date, subsequent refills of the prescribed opioid, and new prescriptions for other controlled substances.

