13.0 Withdrawal of Subjects

- 13.1 In the case that subjects do not complete their follow-up phone interviews and do not respond to 3 calls attempting to re-schedule, they will be withdrawn from the study. Additionally, if subjects exhibit inappropriate or violent behavior towards research personnel, they will be withdrawn from the study.
- 13.2 If a subject decides to withdraw from the study, there will be instructions in the consent document (all patients provided signed copy) with information regarding contacting the study coordinator or PI to withdraw their consent.

EHR-Based Medication Complete Communication (EMC²) Strategy to Promote Safe Opioid Use: A Physician Randomized Trial

13.3 If a subject withdraws from the study the data collected to that time point will be retained to assess for bias in the final sample. They will not be contacted further for interviews.

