24.0 Confidentiality

24.1 Patients. After identifying eligible subjects, a member of the research staff will approach the patient and obtain written informed consent. Written consent will consist of permission to be contacted for the future phone interviews, permission for possible receiving additional information about their medication, and permission for medical record review. The research assistant will review the consent with participants. He/she will provide participants with information on the study plan and their rights as research participants. Participants' consent will be documented by their signatures. Subjects will be provided with a copy of the consent. They may withdraw at any time during the study without penalty or loss of any healthcare benefit or service to which they are entitled.

Patients who state that they do not want to receive further communication via SMS text-messaging will have the opportunity to cancel the text messages and not receive further outreach; they will be included in outcome assessments.

Data from the Illinois Prescription Monitoring Database will be obtained via individual patient record query for the enrolled patients. No protected health information will not be sent outside of Northwestern or to the State for a database query.

Patients will be assigned a unique identification number; The research database will be password protected and accessible only to the research team. Information linking subjects with their unique identifier will be kept on a separate password-protected desktop computer in a locked office within the Department of Emergency Medicine. We believe that in using these methods we will be compliant with the "Standards for Privacy of Individual Identifiable Health Information" under the Health Insurance Portability and Accountability Act of 1996 (HIPAA) Privacy Rule.

ED physicians, mid-level providers and follow-up providers

All participants will be told that their participation is voluntary; they can stop at any time, and whether they participated or not will not be disclosed to their superiors.

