Statistical Analysis Plan

EHR-Based Medication Complete Communication Strategy to Promote Safe Opioid Use

NCT02431793

Document Date: June 7, 2019

Analysis Plan – Main Manuscript

Descriptive statistics were calculated for all socio-demographic, ED visit, and opioid prescription characteristics. Chi-square, one-way Analysis of Variance (ANOVA), and Wilcoxon rank-sum tests were used, as appropriate, to test for balanced randomization. An inter-cluster correlation assessment was conducted to assess the degree of independence among individuals in the same cluster. We used generalized linear mixed models on all outcomes adjusting for physician clustering. Models were run for dichotomous outcomes (safe demonstrated dosing, safe actual dosing; adjusted odds ratios [ORs] reported) and for continuous composite knowledge score (adjusted mean differences reported). Examination for possible associations between patient characteristics and outcome variables revealed significant was conducted, and all models controlled for covariates that related to the outcome. To isolate the effect of the SMS texting portion of the intervention from the EMC² EHR embedded tools a generalized linear mixed model was conducted utilizing two dummy variables (“emc2” for patients in both intervention arms, “text” for patients in EMC² +SMS arm) rather than the study arms on the primary and secondary outcomes as well as the individual knowledge or behavior questions linked to each text message. Significance for all analyses was set at $p < 0.025$ to adjust for multiple testing.

All analyses were first conducted using an intent-to-treat approach. Subsequently, because some patients did not receive one or more pieces of the intervention, the primary outcome was analyzed per-protocol, where the same methodology described previously was used but applied only to patients who successfully received all patient-facing pieces of the intervention. Patients in the EMC² arm were included in the per-protocol analysis if they received the MedSheet and the patient-centered TWS prescription wording on their bottle. Those in the EMC² +SMS arm were included in the per-protocol analysis if they received the MedSheet, TWS prescription wording on bottle, successfully enrolled in SMS texting, and received all seven text messages.

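### Protocol 13.1 and 13.3 treat unanswered calls as withdrawal and do not say that these patients' observed outcomes stay in the intent-to-treat analysis or that record follow-up continues

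*Protocol*

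**What the plan says.** Protocol 13.1 covers patients who have not completed their follow-up interviews: if they "do not respond to 3 calls attempting to re-schedule, they will be withdrawn from the study". Section 13.2 deals separately with a subject who decides to withdraw. Section 13.3 then sets what follows withdrawal: "the data collected to that time point will be retained to assess for bias in the final sample", and "They will not be contacted further for interviews". It does not say whether it applies to 13.1, to 13.2 or to both.

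Other parts of the plan describe wider collection and analysis:

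- **Hospital and ED return data** (Protocol 9.4, Sources of Materials): "data will be abstracted from medical records for all patients enrolled into the study".
- **Prescription-monitoring data** (Protocol 24.1): these "will be obtained via individual patient record query for the enrolled patients". Protocol 8.1 times the pull from the Illinois "Prescription Monitoring Program (ILPMP) at 1-year post initial ED prescription".
- **Analysis set** (Protocol 11.1): subjects with complete information are analysed, with 80% completion of the interview instrument as the example. Withdrawal is not listed as an exclusion.
- **SAP, Analysis Plan**: "All analyses were first conducted using an intent-to-treat approach". The intent-to-treat set is not defined, and withdrawn patients are not mentioned.

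The primary endpoint is measured at the 7-14 day call (Protocol 8.1), before the 1-month call.

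**The concern.** Section 13.3 gives the retained data one purpose, a check for bias in a final sample. If a withdrawn patient's data are used to check that sample, the natural reading is that the patient is outside it. Because 13.1 places unanswered calls under the same label as withdrawal, three things could follow.

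1. A patient who completes the dosing exercise at 7-14 days and misses the 1-month call could lose a primary outcome that was already observed. This sequence is foreseeable: Protocol 9.2 and 22.5 list gift cards for enrolment and the first two calls, and none for the last.
2. A patient unreachable at 2-4 days could be withdrawn and never receive the call at which the primary endpoint is measured.
3. Return visits, admissions and the 1-year prescription indicators need no patient contact and could cover all enrolled patients. They could instead be confined to people who kept answering the phone, a selection made after randomisation and plausibly related to opioid use.

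The plan expects roughly 46% of patients not to be retained at 7-14 days, so the handling of non-responders is not a marginal matter.

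**Working it through.** **Step 1: the plan's own figure.** Protocol 11.1 gives 1500 enrolled, at least 54% retained, and 816 available (272 per arm, 8 per physician). 1500 × 0.54 = 810, within 1% of 816. With 34 physicians per arm, 34 × 8 × 3 = 816 exactly, and 816/1500 = 54.4%. The figure is reproduced.

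**Step 2: patients whom the non-response rule could reach.** 1500 − 816 = 684, and 684/1500 = 45.6%. This is an upper bound for loss through the 7-14 day call at planned retention, since not every missed call ends in withdrawal. The documents give no retention figure for the 1-month call.

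**Step 3: record-based outcomes.** Under Protocol 9.4 and 24.1 the set is 1500/3 = 500 per arm. Under a literal cut-off it could fall to 272. The ratio of standard errors is √(500/272) = 1.356.

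To illustrate selection, assume an indicator occurs in 5% of responders. If non-responders also have 5%, nothing changes. If they have 10%, the full-cohort rate is 0.544 × 5% + 0.456 × 10% = 7.3%, against 5.0% reported. Both rates are assumptions. The result concerns a pooled prevalence and says nothing about a difference between arms.

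**Step 4: primary outcome.** The documents do not say how many 7-14 day completers would be withdrawn at 1 month, so losses of 0% to 20% are assumed. Power uses the planned difference of 0.118 and 2.5% per comparison (Protocol 11.2), taken as two-sided in line with 11.1. With m patients per arm and an ICC of 0.001, the design effect is 1 + (m/34 − 1) × 0.001, so n = m / design effect. At no loss this is 272/1.007 = 270.1. Then

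power = Φ{[0.118√n − z√(2p̄(1−p̄))] / √(p₁(1−p₁) + p₂(1−p₂))}, with z = 2.241.

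The text available does not give the usual-care rate, so the stated 82% can be neither confirmed nor rejected. It is reached near 0.196 vs 0.314 or 0.687 vs 0.805. Results for three assumed usual-care rates (0.441 is close to where power is lowest):

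| Completers removed | Total n | 0.20 vs 0.318 | 0.441 vs 0.559 | 0.60 vs 0.718 |
|---|---|---|---|---|
| 0% | 816 | 81.5% | 69.3% | 74.4% |
| 5% | 775 | 79.3% | 66.8% | 72.0% |
| 10% | 734 | 76.9% | 64.2% | 69.4% |
| 20% | 653 | 71.4% | 58.5% | 63.7% |

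Whatever the starting rate, removing 10% of completers costs about 5 points of power and removing 20% costs 10 to 11.

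**Step 5: the texts side by side.** Section 13.3 speaks of data up to withdrawal and a final sample. Protocol 9.4 and 24.1 speak of enrolled patients, 11.1 of subjects with complete information, and the SAP of intent-to-treat. Section 11.1 does not say which interview its completeness example refers to. Nothing says which text governs when a patient is withdrawn for not answering.

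**The case against.** The strongest reply is that 13.3 is being asked to say more than it does. A reader might infer that it cuts off all data at withdrawal and keeps earlier data for bias assessment alone. The documents do not support that as a stated rule. The section gives a purpose without calling it exclusive, and the only thing it expressly ends is interview contact. No sentence stops a record or prescription-monitoring query, and a patient who misses calls is still enrolled. Return visits are also examined for patients who were never approached for consent (Protocol 28.1 and 29.1), so it would be odd to drop a consented non-responder. All of this stands.

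Scope is also open. Section 13.1 is written in the passive, while 13.2 and 13.3 speak of a subject who decides to withdraw, so 13.3 may have been meant for withdrawn consent. Section 13.1 refers to interviews in the plural, so it is unclear that one missed call triggers it. For the primary outcome, 11.1 counts patients at the 7-14 day call as available for analysis, and the SAP's target is completion of the 1-2 week interval. Both favour keeping an outcome observed before a missed 1-month call.

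Finally, the record-based outcomes are exploratory (Protocol 8.1) and do not appear in the SAP. They are not the only check on self-report either, since the primary endpoint is a demonstrated task.

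These points limit how much can be claimed, but they do not remove the conflict. They show where the rest of the plan leans, while 13.1 and 13.3 read naturally lean the other way, and no sentence reconciles the two. The protocol can supply such a sentence where it wants to: 24.1 expressly keeps patients who cancel text messages in the outcome assessments.

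**Conclusion.** The point holds as an unreconciled conflict. The plan merges non-response with withdrawal. It does not say whether outcomes observed before withdrawal enter the intent-to-treat analysis, whether later calls are attempted, or whether record-based collection continues. Applied as naturally read, 13.1 and 13.3 could select patients on phone response. Actual loss is possible and has not been shown.

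The sizes are conditional:

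- For the exploratory record-based outcomes, 684 of 1500 and the 1.36-fold wider intervals are upper bounds resting on a literal cut-off at planned 7-14 day retention. If 9.4 and 24.1 govern, the loss of this kind is zero.
- For the primary outcome, the cost depends on an unstated share of completers withdrawn later. The power figures show a range under assumed event rates and losses, and are not a forecast.
- No between-arm bias has been demonstrated.

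A correction is worth making because planned non-retention is high and the remedy is cheap and in keeping with the rest of the plan.

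**What to change.** Amend Protocol 13.1 and 13.3, and add matching text to the SAP:

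1. Non-response to calls is a missed interview, not a withdrawal. Later scheduled calls, including the 7-14 day call, are still attempted.
2. All outcomes observed before a missed call or a withdrawal are analysed in the randomised arm under intent-to-treat.
3. Return-visit, admission and 1-year prescription-monitoring data are collected for all enrolled patients except those who revoke record access, as the consent allows. The consent form was not available for this review, so the wording should be checked against it.

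The SAP is written in the past tense, so it should also record which rule was in fact applied to withdrawn patients.

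The cost is a few sentences, some additional call attempts, and prescription-monitoring look-ups by staff who already run them.

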14.0 Risks to Subjects

14.1 Patients who receive care at the participating Emergency Department during this study will be subject to minimal risk through their participation. It is possible that subjects may feel shame and/or some emotional discomfort when taking the literacy and medication use assessments, and performing medication related tasks. We will also be making changes to how their medication instructions are written, and learning through follow-up interviews how they are implementing regimens. If we find that patients in any study arm are misusing medications, we will have a structure in place to address these concerns. This will be documented accordingly within internal study documents; however will not become a part of the medical record unless patients require acute care for their drug misuse or abuse. Consent forms will also acknowledge this disclosure.

Patients in one study arm will receive automated text messages that some could view as intrusive; however they will have the ability to opt-out of the messages at any time. With SMS texting via cell phones, only the phone number is entered into the automated texting system, and no other patient information. We will uphold patient confidentiality and respect any requests to turn off this function during the study.

Subjects will be informed that participation in any part of this research study may result in a loss of privacy, since persons other than the investigators may view their study records if deemed necessary for oversight purposes. However, they will be identified by a unique identification number (“study number”), not by name, and any other identifying information (e.g. personal and/or contact information) will be kept separate from the other data; All information will be kept in secure, password protected files. Further, subjects will be told that unless required by law, only the study investigators, members of the project staff, and representatives of the Northwestern University or clinic Institutional Review Boards will have the authority to review any study records. In such case, they too will be required to maintain confidentiality.

15.0 Potential Benefits to Subjects

15.1 It is possible that subjects enrolled in the two intervention study arms may directly benefit in that they may have, as a result of this study, a better functional understanding of their opioid medication. The results of this study may provide important information regarding how strategies can be implemented via mobile technologies and the

EHR-Based Medication Complete Communication (EMC²) Strategy to Promote Safe Opioid Use: A Physician Randomized Trial

EHR to support safe and appropriate opioid use. Findings of the ED's ability to implement this intervention (and the cost associated) can help similar organizations improve patient education about the safe use of opioids in the future.

16.0 Vulnerable Populations

N/A

17.0 Community-Based Participatory Research

N/A

18.0 Sharing of Results with Subjects

18.1 No results will be shared with subjects. Patients' primary care providers may become aware that they are enrolled in a study through an EHR-notification, however this will not contain any study results—simply a note that the patient received a prescription for Norco and was counseled about it in the ED using the MedSheet.

19.0 Setting

19.1 Patients will be identified, consented and all procedures will be performed in either the Northwestern Emergency Department or over the phone with the participant.

20.0 Resources Available

20.1 The research team is comprised of has 5 PhD level researchers, 3 Physician-researchers (all of whom hold research masters degrees), a research-pharmacist, and a group of research assistants and statistical analysts (who have 2-10 years of experience working on similar projects). We have significant experience in recruiting patients from the emergency department, conducting studies related to medications (including the medication being studied), consenting patients to follow-up, and conducting multi-part follow-up with both in-person and telephone interviews. Additionally, the team has experience in managing data in accordance with the best-practices of the IRB to protect patients' confidentiality.

20.2 Initial estimates suggest that approximately 9,000 subjects will be potentially eligible for follow-up annually (representing 16% of discharged patients from the ED).

The PI has 30% protected time for this study throughout the study duration and full support of the Department of Emergency Medicine. The Co-Is have ample time supported to assist in weekly meetings, data analysis, DSMB review, and other study operational tasks. The three physician-researchers will be available at all hours for the RAs to contact if there are any concerns related to the safety protocol (see attached).

EHR-Based Medication Complete Communication (EMC²) Strategy to Promote Safe Opioid Use: A Physician Randomized Trial

The study team will have 2 full-time RAs dedicated to enrolling and completing follow-up on the study with support from a team of other RAs to cover evening and weekend hours.

Facilities: The patients will be approached and consented for participation while in the Emergency Department. Follow-up calls by the RAs will occur at a time of convenience for the patient and the RAs have access to closed offices wherein to conduct the calls and record data.

All persons assisting in the project will be adequately informed about the research protocol, the research procedures, and their duties and functions. We will ensure this by conducting weekly research meetings (already in-place) and by reviewing key concepts and conducting practice sessions for the consent process and interviews.

